2. OBJECTIVES AND ENDPOINTS

The main objective of this study (*Part 1 and Part 2*) is to continue to collect long-term safety and tolerability data in participants with AD treated with gantenerumab. Specific objectives and corresponding endpoints for the study are outlined in [Table 1](#).

Table 1 Objectives and Corresponding Endpoints

Safety Objective	Corresponding Endpoints

 • To evaluate the long-term safety and tolerability of continued treatment with SC gantenerumab at target dose in participants with AD who received gantenerumab in OLEs of Studies WN25203 or WN28745 	
 • Nature, frequency, severity, and timing of AEs and SAEs • Physical examinations (including neurological systems), vital signs, blood tests, ECGs, and C-SSRS • Nature, frequency, severity, and timing of MRI findings: ARIA-E and ARIA-H • Nature, frequency, severity, and timing of injection-site reactions • Immunogenicity of long-term treatment with gantenerumab through the measurements of ADAs • Incidence of treatment discontinuations for AEs • Incidence of AEs of special interest
Exploratory Efficacy Objective	Corresponding Endpoint

 • To assess the long-term clinical effect in participants with AD 	
 • MMSE total score will be used to assess AD progression

Table 1 Objectives and Corresponding Endpoints (cont.)

Exploratory Pharmacodynamic Biomarker Objective	Corresponding Endpoints

• To evaluate the long-term effect of gantenerumab in participants with AD	
• MRI-derived measurements over time, such as volumetric changes in whole brain, ventricles, hippocampus, or other structures, in all participants• Plasma pharmacodynamic biomarkers over time

AD = Alzheimer's disease; ADA = anti-drug antibodies; AE = adverse event; ARIA-E = amyloid-related imaging abnormalities–edema/effusion; ARIA-H = amyloid-related imaging abnormalities–hemosiderin deposition; C-SSRS = Columbia-Suicide Severity Rating Scale; ECG = electrocardiogram; MMSE = Mini Mental State Examination; MRI = magnetic resonance imaging; OLE = open-label extension; SAE = serious adverse event; SC = subcutaneous

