3.3.5.2 Brain Volumetry

A characteristic feature of AD is neuronal destruction. Such neuronal loss is demonstrated at a macroscopic level by progressive cerebral atrophy, which can be tracked on MRI (Fox and Kennedy 2009). Multiple changes in brain anatomy beyond those associated with normal aging have been reported in participants with AD (e.g., enlarged ventricles, decreased cortical thickness, decreased total brain volume, and hippocampal atrophy), and there is evidence for strong correlations between these imaging biomarkers and functional cognitive measures (Mungas et al. 2005; Li and Wahlund 2011). Based on volumetric MRI measurements, the two most established markers of disease progression through longitudinal observational studies are hippocampal and whole brain atrophy (Fox et al. 2000; Fox et al. 2005; Jack et al. 2010), with ventricular expansion being a third and related quantitative marker.

Therefore, to quantify the effects of gantenerumab on neurodegeneration, whole brain volume, ventricular enlargement, and regional brain volume changes will be assessed at baseline and following long-term treatment with gantenerumab. All MRI reads and volume measures will be conducted by the central reader.

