4.5.9 Brain Magnetic Resonance Imaging

The MRI should be performed using 1.5-T or 3.0-T scanners, and the same scanner is strongly preferred for an individual participant for the full duration of the study. Only scanners approved for use in the study should be used. MRI will be conducted at baseline for safety monitoring prior to dosing and for structural brain volumes measures. Magnetic resonance imaging will be used during the study to help assess safety such as the occurrence of microbleeds or signs potentially indicative of inflammation or ARIA-E. Additional unscheduled MRI scans may be utilized to better understand relevant CNS related-adverse events (such as increased confusion) or to follow a sign that emerges at a scheduled scan; contrast agent may be used in such a case of follow-up if administration of contrast agent is considered safe for the participant according to local standards.

MRI scans will include the following sequences:

- 3D T₁-weighted gradient recalled echo (GRE) scans
- T₂*-weighted GRE scans
- T₂-weighted fluid-attenuated inversion recovery (FLAIR) scans

The MRI will take approximately 30 minutes to complete.

The MRI scans will be reviewed by a central MRI core laboratory, which will perform the diagnostic reads and assessment of MRI outcome measures. Magnetic resonance imaging scans should preferably be transferred to the central MRI core laboratory electronically. Data transfer from individual study sites to the central MRI core laboratory may take up to 7–10 days, if not done electronically. Upon receipt of the MRI scans from the study sites, the central MRI core laboratory will provide the diagnostic reads. MRI results must be made available to investigators prior to *the next dosing visit*.

The MRI facility qualification and scan quality control will be performed by the central MRI core laboratory.

The MRI scan performed for the follow-up visit in Studies WN25203 and WN28745 will be used as baseline scan in this study, where possible. In case there might be a gap between follow-up visit from OLEs of WN25203/WN28745 and the first dose in this study of more than six months MRI has to be repeated.

Additional instructions regarding the procedures for MRI facility qualification and MRI scan acquisition and transmittal to the central reading facility can be found in the MRI Manual.

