- b Informed consent should be obtained by the participants before any study procedures are performed, and may be obtained while they are active in the qualifying study; however, enrollment in this study is contingent upon completion of the qualifying study, and any premature discontinuation of study participation or study drug in the qualifying study, or failure to meet any other eligibility criterion (see Section [4.1.1](#)), precludes enrollment in this study.
- c MRI results should be available before dosing on Day 1. At subsequent visits indicated in the schedule, MRI scans must be performed within 20 days after dose administration and results made available and reviewed before the next scheduled dose. Participants will be asked if they experience CNS adverse events up to one week before each MRI is performed.
- d Includes volumetric outcome measures.
- e Vital signs include HR, BP, and *temperature*. The same arm should be used for all blood pressure measurements. HR and BP should not be measured unless 15 minutes have passed since the last blood draw. Weight will be recorded yearly at the time of physical examination.
- f Perform after the participant has been in a supine position for 5 minutes. ECGs for each participant should be obtained at baseline and any time during the study if deemed necessary by the investigator from the same machine whenever possible and performed prior to any blood draws, brain MRI scans.

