Appendix 1 Schedule of Activities (Part 1 and Part 2)

- ^g Serum chemistry includes AST/SGOT, ALT/SGPT, alkaline phosphatase, total protein, total bilirubin, serum albumin, CPK, sodium, potassium, calcium, BUN, and serum creatinine (and creatinine clearance calculated by the central laboratory).
Hematology includes hemoglobin, hematocrit, red blood cell (with morphology), WBCs, platelet, basophil, eosinophil, lymphocyte, monocyte, neutrophil, and WBC–other total counts.
- ^h At all visits where biomarker plasma, PK, and ADA samples are needed, the samples should be obtained before administration of gantenerumab if applicable. Accurate recording of the time of study drug administration and PK sampling is critical.
- ⁱ Female *participants* of childbearing potential (including those who have had a tubal ligation) must have a urine pregnancy test performed at the site prior to each dose administration. If a urine pregnancy test is positive, it must be confirmed by a serum pregnancy test at the central laboratory.
- ^j C-SSRS (since last visit) should be obtained every 6 months *and additionally* at any time deemed necessary by the investigator.
- ^k *Only the relevant assessments will be performed, determined per the investigator’s clinical judgment, and do not necessarily include all those listed above.*
- ^l *MRI must be performed within 20 days after dose administration and results made available and reviewed before the final follow-up or drop-out visit to allow review before the final visit. Participants will be asked if they experience CNS adverse events up to one week before each MRI is performed.*

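### The early-termination MRI is not marked for brain volumetry, so participants who leave before Week 52 have no planned post-baseline volume

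*Combined protocol and SAP*

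**What the plan says.** **Which scans are volumetric.** In the Appendix 1 schedules, footnote d ("Includes volumetric outcome measures") is on the MRI at Day 1, Week 52 and Week 104 in Part 1, and at Weeks 104, 156 and 208 in Part 2. The MRIs at Weeks 24, 76, 128 and 180 do not carry it.

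**The exit scan.** An MRI is scheduled at Follow-Up/Early Termination, with footnote l only: "MRI must be performed within 20 days after dose administration and results made available and reviewed before the final follow-up or drop-out visit". That footnote covers timing and review and does not mention volumes.

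**What is acquired.** Section 4.5.9 introduces its list with "MRI scans will include the following sequences", names a 3D T1-weighted scan first, and does not limit the list to particular visits. On purpose, it says "MRI will be conducted at baseline for safety monitoring prior to dosing and for structural brain volumes measures", and of later scans "Magnetic resonance imaging will be used during the study to help assess safety".

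**The endpoint.** Table 1 in Section 2 gives the exploratory pharmacodynamic endpoint as "MRI-derived measurements over time, such as volumetric changes in whole brain, ventricles, hippocampus, or other structures, in all participants". Section 3.3.5.2 adds that "regional brain volume changes will be assessed at baseline and following long-term treatment with gantenerumab".

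**The analysis.** Section 6.7 is one sentence naming volumetric MRI change as an exploratory biomarker analysis. It gives no visits, no estimator and no rule for early leavers.

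**The parallel endpoint.** The other endpoint under the same objective is plasma biomarkers. Section 4.5.6 and Appendix 1 collect these at baseline, yearly, at the end of the study and also at early termination.

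**The concern.** Change in volume needs at least two volumes. A participant who leaves before Week 52 is planned to have one, even though an exit MRI is scheduled and the general sequence list includes the scan type that volumetry uses. A participant who leaves between later annual scans contributes nothing on volume for the time since the last of them.

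The plan treats the two endpoints under this objective differently without saying why: plasma biomarkers have an exit value and volumes do not. The omission therefore looks unintended.

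At stake is whom the volumetric summary describes. Leaving may be related to disease course. Section 4.6.1 lets the investigator or Sponsor stop treatment in the participant's best interest, and Section 4.1.3 carries into Part 2 the exclusion for those judged unlikely to benefit, for instance because of progression. If faster decliners leave more often, a summary that omits their exit volumes leans toward slower atrophy. The documents give no data on whether this happens.

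**Working it through.** The plan states no figure to reproduce here. The 116 is a count of rollover participants, and volumetry has no power calculation.

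**Step 1: count the scans (Appendix 1).** Scheduled MRIs fall at Weeks 0, 24, 52, 76, 104, 128, 156, 180 and 208, which is 9. Those with footnote d fall at Weeks 0, 52, 104, 156 and 208, which is 5. In Part 1 alone, 3 of 5 are marked. The Follow-Up/Early Termination MRI is not.

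**Step 2: participants with no planned post-baseline volume.** Inputs are N = 116 (Section 6.1) and an annual dropout d. The documents give no dropout rate, so d is an assumption, taken as constant over time and varied from 5% to 30%.

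- Leave before Week 52: 116 × d
- Leave before Week 24, so the exit scan is the only post-baseline MRI: 116 × [1 − (1 − d)^(24/52)]
- Leave between Weeks 24 and 52, so the Week 24 scan also exists: the difference
- Leave before Week 104: 116 × [1 − (1 − d)²]

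| Assumed d | Before W52 | of which before W24 | of which W24 to W52 | Before W104 |
|---|---|---|---|---|
| 5% | 5.8 | 2.7 | 3.1 | 11.3 |
| 10% | 11.6 | 5.5 | 6.1 | 22.0 |
| 20% | 23.2 | 11.4 | 11.8 | 41.8 |
| 30% | 34.8 | 17.6 | 17.2 | 59.2 |

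For example, at d = 10%: 116 × 0.10 = 11.6, and 116 × (1 − 0.90²) = 116 × 0.19 = 22.0.

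The column headed W24 to W52 shows that mid-year reads alone would not close the gap. About half of those without a post-baseline volume leave before Week 24 and have only the exit scan.

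**Step 3: age of a leaver's last planned volume.** With constant dropout, the mean time from the last annual scan to leaving is 52/(−ln(1 − d)) − 52(1 − d)/d weeks. At d = 5% this is 1013.8 − 988.0 = 25.8 weeks. At d = 30% it is 145.8 − 121.3 = 24.5 weeks. The maximum is just under 52 weeks.

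**Step 4: completers.** Footnotes c and l each place the scan within 20 days after a dose. For someone finishing at Week 104 or Week 208, the annual scan and the follow-up scan both refer to the same last dose. A volumetric read of the follow-up scan then adds little, and the gain is confined to early leavers.

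**The case against.** **The endpoint wording is satisfied.** A reader might infer from Table 1's reference to all participants that a post-baseline volume is promised for everyone, so that the endpoint fails. The documents do not support that. The phrase most naturally says who is measured. It fixes no timepoint and no completeness requirement, and yearly reads fit the timing given in Section 3.3.5.2. This objection stands.

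**Nothing is lost.** A reader might also infer that data on file are thrown away. An unmarked scan still exists, no text forbids reading it, and Section 4.5.9 gives the core laboratory the MRI outcome measures without naming visits. What is missing is a planned read. This also stands.

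**The scan may not be fit for volumetry.** Section 4.5.9 refers acquisition detail to an MRI Manual that is not among the documents, and it names volumes as a purpose only for the baseline scan. So the general sequence list makes an exit read feasible on its face but does not prove adequate quality. This stands as a condition on the fix.

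**Annual volumetry is a legitimate choice.** A reader might want all nine scans read for precision. The sum of squares of scan times is 10.0 years² for the five annual scans and 15.0 for all nine, so the measurement-error part of one completer's slope variance would fall by 1 − 10.0/15.0 = 33%, and its standard error by 18%. But that covers completers and one variance component. Between-participant variation in slope is unaffected, and the documents give neither component, so the gain for mean atrophy is unknown. Mid-year reads and a particular mixed model are preferences for an exploratory endpoint.

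**Bias is not shown.** Section 6.7 names no estimator, the study has no control arm, and eligibility already selects people who completed the parent extensions on drug. Direction and size of any bias cannot be established. What remains is that, with no planned exit volume, a participant who leaves before Week 52 has no planned change value under any estimator.

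**Conclusion.** The point holds as a limited gap in the schedule. Appendix 1 plans volumes at baseline and yearly but not at the exit MRI it already schedules, while the parallel plasma endpoint is collected at exit and Section 6.7 has no rule for early leavers. Followed as written, leavers before Week 52 contribute no volume change, and later leavers contribute nothing after their last annual scan.

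The number affected cannot be derived from the documents. It is about 6 to 35 of 116 without a post-baseline volume if annual dropout is 5% to 30%, and that range is entirely an assumption. A second assumption is that footnote d marks where volumes will be read; no sentence says the other scans will not be.

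The documents do not support a finding that the endpoint is unmet, that images are lost, or that mean atrophy is biased by a known amount. With an exploratory endpoint and no test planned for it, this is a cheap improvement of low severity.

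**What to change.** - In both Appendix 1 schedules, add footnote d to the Follow-Up/Early Termination MRI for participants who leave early. Completers can be exempted, since their Week 104 or Week 208 scan serves the purpose.
- In Section 6.7 or the analysis plan, state that this read enters the volumetric change analysis at its actual scan date, and that the number of participants without any post-baseline volume will be reported.
- Volumetric reads at Weeks 24, 76, 128 and 180 are optional.

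**Cost.** Central-reader processing of one already scheduled scan per early leaver, with no new visit or scan. In Part 1 that is about 11 to 59 reads under the assumed dropout (leavers before Week 104), and it cannot exceed 116 over the whole study. Adding the four mid-year reads would bring up to 4 × 116 = 464 more.

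**Limits.** The scan must meet volumetric acquisition quality. Participants are asked to return for the exit visit, and Section 4.6.2 rules out follow-up once consent is withdrawn, so some leavers will still have no exit scan.

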Appendix 1 Schedule of Activities (Part 1 and Part 2)

- ^g Serum chemistry includes AST/SGOT, ALT/SGPT, alkaline phosphatase, total protein, total bilirubin, serum albumin, CPK, sodium, potassium, calcium, BUN, and serum creatinine (and creatinine clearance calculated by the central laboratory).
Hematology includes hemoglobin, hematocrit, red blood cell (with morphology), WBCs, platelet, basophil, eosinophil, lymphocyte, monocyte, neutrophil, and WBC–other total counts.
- ^h At all visits where biomarker plasma, PK, and ADA samples are needed, the samples should be obtained before administration of gantenerumab if applicable. Accurate recording of the time of study drug administration and PK sampling is critical.
- ⁱ Female *participants* of childbearing potential (including those who have had a tubal ligation) must have a urine pregnancy test performed at the site prior to each dose administration. If a urine pregnancy test is positive, it must be confirmed by a serum pregnancy test at the central laboratory.
- ^j C-SSRS (since last visit) should be obtained every 6 months *and additionally* at any time deemed necessary by the investigator.
- ^k *Only the relevant assessments will be performed, determined per the investigator’s clinical judgment, and do not necessarily include all those listed above.*
- ^l *MRI must be performed within 20 days after dose administration and results made available and reviewed before the final follow-up or drop-out visit to allow review before the final visit. Participants will be asked if they experience CNS adverse events up to one week before each MRI is performed.*

Appendix 2 Management Rules for Amyloid-Related Imaging Abnormalities

Event	Characteristics	Action to be Taken
ARIA-E	Asymptomatic ARIA-E ≥ 1 and < 4 BGTS	
Participants who had MRI on target dose:
 
 • Continue study drug at the same dose level and perform MRI scans at 4-week intervals until ARIA-E resolves, then resume the standard MRI schedule (Appendix 1) 
Participants who had MRI prior to up-titration to target dose:
 
 • Continue study drug and do not up-titrate. Repeat MRI scan 4 weeks later • As long as BGTS is < 4 and ≥ 1, continue study drug at the same dose level and continue MRI monitoring at 4-week interval • Once ARIA-E resolves, complete up-titration to target dose and resume the standard MRI schedule (Appendix 1)
	Symptomatic ARIA-E (of any size) or asymptomatic ARIA-E and BGTS ≥ 4	
Participants who had MRI on target dose:
 
 • Temporarily interrupt study drug and perform MRI scans at 4-week intervals until symptoms and ARIA-E resolve • When symptoms and ARIA-E resolve, reintroduce study drug at target dose and resume the standard MRI schedule (Appendix 1) 
Participants who had MRI prior to up-titration to target dose:
 
 • Temporarily interrupt study drug and perform MRI scans at 4-week intervals until symptoms and ARIA-E resolve • When symptoms and ARIA-E resolve, reintroduce study drug at the dose level given at the time the event was detected • After one dose at the dose level given at the time the event was detected, but before the next scheduled dose, perform a subsequent MRI scan • If no new ARIA-E is detected, then complete up-titration to target dose and resume the standard MRI schedule (Appendix 1)
	Any recurrence of ARIA-E	
 • Treat as above (based on symptoms and BGTS)
ARIA-H	Any disseminated LH (more than 3 focal LH)	
Permanently discontinue study drug
 
Note: In the absence of disseminated LH, study drug can be continued, including up-titration to target dose

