4.6 TREATMENT, PARTICIPANT, STUDY, AND SITE DISCONTINUATION

4.6.1 Study Treatment Discontinuation

Participants must discontinue study treatment if they experience any of the following:

- Any medical condition that the investigator or Sponsor determines may jeopardize the participant's safety if he or she continues to receive study treatment
- Investigator or Sponsor determination that treatment discontinuation is in the best interest of the participant
- Pregnancy
- Upon evidence of any disseminated leptomeningeal hemosiderosis (i.e., more than three focal leptomeningeal hemosiderosis)
- Upon evidence of intracerebral macrohemorrhage

All participants who withdraw from treatment will be asked to return 4 weeks after last dose to complete the early termination visit assessments.

The primary reason for study treatment discontinuation should be documented on the appropriate eCRF.

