5. ASSESSMENT OF SAFETY

5.1 SAFETY PLAN

Gantenerumab is not yet approved, and clinical development is ongoing. The safety plan for participants in this study is based on clinical experience with gantenerumab in completed and ongoing studies. The identified risks for gantenerumab are outlined below. Please refer to the gantenerumab IB for a complete summary of safety information.

Several measures will be taken to ensure the safety of participants in this study. Eligibility criteria have been designed to exclude participants at higher risk for imaging related abnormalities. Participants will undergo safety monitoring during the study, including assessment of the nature, frequency, and severity of adverse events. In addition, guidelines for managing adverse events, including criteria for dosage modification and treatment interruption or discontinuation, are provided below.

Participants should be observed for a minimum one-hour post IMP administration. Rescue medications to treat anaphylactic and anaphylactoid reactions must be available at the site or at the dosing location for MN visits. Participants and their study partners will be alerted to watch for signs of anaphylactic and anaphylactoid reactions and to contact the study center as soon as possible if any such signs are noted (refer to the pharmacy manual).

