5.1.1 Risks Associated with Gantenerumab

5.1.1.1 Amyloid-Related Imaging Abnormalities

Amyloid-related imaging abnormality is the most significant adverse event reported with therapies against aggregated forms of A β . These findings are dose-, time-, and APOE ϵ 4 allele-dependent (Piazza and Winblad 2016).

The mechanism underlying the development of ARIA-E and ARIA-H during anti-amyloid treatment is unknown. Because antibodies target removal of A β from both the parenchyma and cerebral vasculature, vessels with preexisting amyloid vascular pathology might become transiently more susceptible to leakage of vascular contents. This pathology results in ARIA-E if the leakage consists of proteinaceous fluid and in ARIA-H if the leakage consists of blood products (Sperling et al. 2012).

Thus, an anti-A β therapy that effectively maintains vascular β -amyloid clearance would allow vascular remodeling and may, with time, decrease the risk of such extravasation events (Sperling et al. 2012). This is consistent with experience in previous and ongoing studies and with reported data from the long-term extension study of aducanumab treatment (Viglietta et al. 2016).

In this study, an MRI scan documenting the absence of disseminated leptomeningeal hemosiderosis will be required prior to first gantenerumab dose. If ARIA findings occur, more intense MRI monitoring, dose adjustments, temporary dose holding, or permanent discontinuation will be implemented according to an ARIA-related dose-adjustment plan, described in Section 5.1.2. Safety findings (including individual participant and aggregate data) will be reviewed on a regular basis by the Roche Internal Monitoring Committee (IMC).

To date, clinical experience with gantenerumab has shown that ARIA events are time, dose, and APOE ϵ 4 dependent. ARIA events are manageable with MRI monitoring and

dose intervention algorithms. In addition, in case of clinical symptoms associated with ARIA-E, the use of IV glucocorticosteroids may be considered.

Rules for management of participants who develop ARIA-E or ARIA-H are provided in [Appendix 2](#).

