5.1.2 Management of Participants Who Experience Selected Adverse Events

For Part 1 of the study, each participant continued to receive SC gantenerumab Q4W at the dose they received in the qualifying study (OLE part of Studies WN25203 or WN28745) and will undergo a brain MRI examination as per Schedule of Activities, with the following exception: Participants who experienced a dosing gap of more than 16 weeks for any reason between the last gantenerumab dose in the qualifying study and first gantenerumab dose in this study may, depending upon whether they previously experienced an ARIA-E event, start dosing at a lower dose and undergo an up-titration step (see [Appendix 3](#)). A brain MRI examination will be required prior to the dose increase (pre-up-titration MRI scan) and then according to the Schedule of Activities once the target dose is reached. The pre-up-titration MRI scan will determine eligibility for the next dose, as described in [Appendix 2](#).

In the case that a participant has at the baseline (*Day 1*) visit an ARIA-E that is ongoing since the qualifying study, there will be a continuity of ARIA management between the two studies, and ARIA management rules as described in [Appendix 2](#) will apply

For ARIA MRI findings detected during the study (Part 1 and Part 2), the dose adjustment and discontinuation rules described in [Appendix 2](#) will apply.

The IMC will review the nature, incidence, severity, and timing of ARIA findings and may recommend adjustment of dosing regimen and/or ARIA management for the overall study population or for a specific APOE ε4 genotype.

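### Does the Appendix 2 ARIA-H note allow dosing to continue after a macrohemorrhage, which Section 4.6.1 makes a mandatory reason to stop?

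*Combined protocol and SAP*

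**What the plan says.** Section 4.6.1 sets the general stopping rule: "Participants must discontinue study treatment if they experience any of the following". Two of its items are imaging findings. One is disseminated LH, meaning more than three focal areas. The other, on its own line, reads "Upon evidence of intracerebral macrohemorrhage". Both findings are also exclusion criteria in Section 4.1.2, and Section 4.1.3 carries those criteria over to Part 2.

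The ARIA-H row of Appendix 2 has one trigger, disseminated LH, and one action, permanent discontinuation. A note in the same cell adds "In the absence of disseminated LH, study drug can be continued, including up-titration to target dose". Neither the table nor its footnotes mention macrohemorrhage or Section 4.6.1.

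The safety chapter sends the reader to Appendix 2 for ARIA. Section 5.1 says that "criteria for dosage modification and treatment interruption or discontinuation, are provided below". Section 5.1.1.1 says that "permanent discontinuation will be implemented according to an ARIA-related dose-adjustment plan, described in Section 5.1.2". Section 5.1.2 begins its rule with "For ARIA MRI findings detected during the study (Part 1 and Part 2), the dose adjustment and discontinuation rules described in" and then names Appendix 2.

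**The concern.** A clinician holding an MRI report and following the ARIA chapter goes from Section 5.1 to 5.1.1.1, then to 5.1.2 and Appendix 2. Nothing on that path leads to Section 4.6.1, which stands earlier in the protocol, and Section 4.6.1 does not mention Appendix 2. At the end of the path is a permission whose only stated condition is the absence of disseminated LH.

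Other text in the chapter can add to the doubt. The sentence on the MRI before first dosing also names LH alone: "an MRI scan documenting the absence of disseminated leptomeningeal hemosiderosis will be required prior to first gantenerumab dose". The account of mechanism says that vascular leakage results "in ARIA-H if the leakage consists of blood products", which could be taken to cover a large bleed as well as a small one. On that reading, a participant with a macrohemorrhage but no disseminated LH would fall under a mandatory stop in one place and a permission to continue in another. A safety stop might then be missed, and Section 5.1.2 keeps Appendix 2 in force for Part 2.

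**Working it through.** No figure is at issue, so the check sets the passages side by side.

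**1. Does macrohemorrhage belong in the ARIA-H row?** Every description of ARIA-H as a finding points to small bleeds or hemosiderin:

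- Section 5.2.4 describes it as suggestive of microhemorrhages, hemosiderin deposits or both.
- Section 1.2.1.1 speaks of hemosiderosis or microbleeds.
- The abbreviation list and the Appendix 2 footnotes expand the term as hemosiderin deposition.
- Section 4.5.9 gives microbleeds and signs of ARIA-E as its examples of what the safety MRI looks for.

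No passage calls macrohemorrhage a form of ARIA. Sections 4.1.2 and 4.6.1 list it as a separate item beside LH. The only text that could suggest otherwise is the phrase on blood products in Section 5.1.1.1, and that sentence explains a mechanism and does not define a category.

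**2. What do the pointers cover?** Those in Sections 5.1.1.1 and 5.1.2 are limited to ARIA findings. They send ARIA to the ARIA table. They do not send macrohemorrhage there unless step 1 is answered the other way.

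**3. What does the note do within its row?** It sits beside the trigger of more than three focal areas of LH and says what follows when that trigger is not met: ARIA-H short of it is not in itself a reason to stop. The other rows work the same way. The row for asymptomatic ARIA-E with a score from 1 to below 4 tells the site to keep dosing and makes no exception for LH. Nobody would read it as cancelling the LH stop in the row for ARIA-H.

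**4. Suppose the row did cover macrohemorrhage.** The four combinations are:

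| Disseminated LH | Macrohemorrhage | Section 4.6.1 | Appendix 2, ARIA-H row | Action that satisfies both |
|---|---|---|---|---|
| yes | yes | must stop | stop | stop |
| yes | no | must stop | stop | stop |
| no | yes | must stop | may continue | stop |
| no | no | no imaging stop | may continue | may continue, as far as this row goes |

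The two texts differ in one of the four. There, stopping meets the obligation and breaches nothing in Appendix 2, because *can* leaves the choice open and *must* does not.

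**5. What else guards the point?** Macrohemorrhage bars entry under Section 4.1.2, and Section 3.1.1 asks for the MRI result before the first dose, so the LH-only sentence on the pre-dose scan leaves no opening. Section 9.5 reports enrollment into Part 1 as having taken place, and Section 6.1 gives 116 participants. For Part 2, Section 4.1.3 reapplies the exclusion, and Sections 3.1.2, 3.3.2 and 4.1 tie entry to Section 4.6.1. The up-titration half of the note concerns restarts after a dosing gap, which Appendix 3 confines to Part 1.

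**6. Would any analysis change?** Section 6.5 plans descriptive summaries of MRI findings and of discontinuations for adverse events. Neither is defined by the wording of the Appendix 2 note.

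**The case for a change.** The best case for a change is that a mandatory stop should be visible where the dosing decision is made, and that the ARIA-H row will be consulted often. Section 1.2.2 reports new ARIA-H in 51 of 154 participants in one parent extension and 75 of 219 in the other. Together that is (51 + 75) / (154 + 219) = 126 / 373 = 33.8%. A participant can have ARIA-H and a macrohemorrhage on the same scan, and even a narrow reading of the row leaves the site looking at a cell that says dosing may go on. The citations of Section 4.6.1 elsewhere concern entry to Part 2, not what to do with an on-study scan. The change would cost only a few words.

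Part of this stands. Appendix 2 and Section 5.1.2 do not repeat or cite the macrohemorrhage stop, and the protocol never says outright whether macrohemorrhage lies inside or outside the ARIA-H row. A cross-reference would do no harm.

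The claim of a conflict does not stand. The 33.8% is a rate of ARIA-H, not of macrohemorrhage, and says nothing about how often the two texts would meet. In the joint case the ARIA-H row still speaks only to ARIA-H, and Section 4.6.1 still requires the stop. That section carries the plain heading for treatment discontinuation, and its first item separately covers any medical condition judged to put the participant at risk. A site needs no interpretation to find the rule there.

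**Conclusion.** No change follows. Section 4.6.1 has two imaging-based mandatory stops and Appendix 2 repeats one of them. That is a missing cross-reference in an ARIA-specific table, not a contradiction. A site following the protocol as written stops study drug on macrohemorrhage, and no participant's treatment, planned summary or conclusion would differ if the link were added.

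This rests on two readings: that ARIA-H means what Section 5.2.4 and the abbreviation lists say, and that an obligation prevails over a permission. The second is enough alone, so the conclusion survives even if macrohemorrhage were placed within the ARIA-H row. How many participants might meet the situation cannot be worked out, since the documents give no macrohemorrhage rate. If the sponsor amends the protocol for other reasons, it could link the passages as an editorial matter. Nothing here judges the clinical merits of either rule.
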